1 STUDY OBJECTIVES

1.1 Primary Objective

To conduct a pilot randomized trial comparing outcomes of inguinal hernia surgery under local versus general anesthesia for adults aged 65 years and older. This will establish feasibility of conducting a multisite randomized trial and will optimize study procedures prior to conducting the multisite trial. We will measure

- (1) Rates of enrollment, percent of eligible patients enrolled, and reasons for non-enrollment
- (2) Proportion of participants completing all study visits
- (3) Proportion of missing data
- (4) Time to complete study evaluations and instruments
- (5) Participant satisfaction with study procedures and instruments
- (6) Whether survey instruments can be eliminated due to redundancy
- (7) Estimated sample size for a fully powered trial

We hypothesize that:

- (1) Based on our preliminary data, at least 75% of eligible patients will agree to be randomized.
- (2) We will be able to follow 100% of patients up to their 2 week postoperative visit (as essentially all patients keep this appointment in our clinical practice), and that we will be able to follow at least 90% of patients at the six month time point.
- (3) Missing data on study instruments will be <5%
- (4) Overall time burden for instrument completion will be acceptable to patients
- (5) One or more study instruments can be eliminated (thus reducing the time burden) because the other instruments may predict a substantial portion of variance
- (6) We will be able to use data from the pilot to estimate the necessary sample size for a multisite randomized trial

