9.1.3 Justification for pilot design

The chances of completing a successful multisite randomized clinical trial are increased by testing study procedures and processes on a smaller scale prior to conducting a fully powered trial.^{18,19} This will enable us to identify and address problems prior to initiating the fully powered study. Conducting a pilot study also allows us to test study instruments and potentially reduce the time burden at each evaluation visit by determining whether study measures are statistically redundant (the other measures explain a substantial portion of one measure's variance). Reducing the time burden for participants is an important step to enhance the completeness of data collection by minimizing missing data and reducing withdrawals from the study.

As outlined below and in the attached grant proposal, data from the pilot study will also be used for preliminary estimation of effect sizes for the future randomized trial. As the pilot is, by definition, not fully powered to detect all relevant differences between groups, this analysis is entirely exploratory.

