 - a. Measurement: At each visit, after completing all other study forms and procedures, participants will be asked to complete a brief 10-item Likert-type score to measure overall satisfaction with the study visit and a similar item assessing satisfaction with the time burden of the instruments. Additionally, we will conduct a brief interview with open-ended questions at the end of each visit asking patients to provide any feedback on the study procedures or instruments. These will not be recorded but field notes by the research assistant will be taken.
 - b. Timing: Assessments will occur at each study visit and will be reviewed at the last team meeting of each month.
 - 6) Outcome: Whether survey instruments can be eliminated due to redundancy
 - a. Measurement: To determine whether we can reduce the survey burden by eliminating redundant measures, we will employ methods outlined by Harrell for data reduction.²² Each survey instrument will be evaluated as the dependent variable in a separate linear regression with the scores of all other instruments used as predictors, along with demographic information. The adjusted R^2 (explained variance) for each regression will be estimated. Any instrument where the R^2 exceeds 40% will be eliminated based on the idea that little additional information is provided by including that instrument (i.e. the other surveys explain a substantial portion of the information contained within that instrument).
 - b. Timing: We will assess survey redundancy once 25% of planned enrollment is achieved and we will measure again at 75% enrollment. This will provide reasonable data stability for estimation and also provide time for us to test study procedures after eliminating any instruments that are found to be redundant.
 - 7) Outcome: Estimating sample size for fully powered trial
 - a. Measurement: For continuous variables, we will estimate means and standard deviations. For categorical variables, we will estimate proportions and 95% confidence intervals.
 - b. Timing: Final sample size estimate will be performed after data collection for the last patient is complete.

Table 2. Analysis of primary (pilot) outcomes		
Outcome	Measurement	Timing
Rate of enrollment and percent of eligible patients enrolled	
 Running count and graph of planned versus actual enrollment 	Team meeting (every other week)

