Reasons for non-enrollment	
 Running count and graph 	Team meeting (every other week)
Proportion of participants completing all visits	
 Running count and graph 	Team meeting (every other week)
Proportion missing data	
 Running count and graph 	Team meeting (every other week)
Time to complete study evaluations and instruments	
 Research assistant uses timer during visit 	Once per month at team meeting
Participant satisfaction with procedures and instruments	
 10-point Likert-type scale Short interview at end of each visit 	Once per month at team meeting
Identify redundant instruments	
 Predict explained variance (R-squared) of each instrument from scores of other instruments 	At 25% and 75% enrollment
Identify areas of improvement for study procedures	
 Short patient interview at end of each visit Study team discussions at weekly meeting 	Team meeting (every other week)
Estimate sample size	
 Measures of dispersion (mean and standard deviation) Proportions and 95% confidence intervals 	After data collection for final patient is complete

State and define the primary outcome measure and specify at which study visit the outcome assessments will be performed.

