9.5 Data Analyses

9.5.1 Analysis of pilot/feasibility outcomes

We will use simple descriptive statistics (counts, ratios, mean/standard deviation, median/interquartile range, dispersion, proportions) to analyze the following outcomes: rate of enrollment and percent of eligible participants enrolled, reasons for non-enrollment, proportion of participants completing all visits, proportion of missing data, time to complete study evaluation and instruments, participant satisfaction.

To determine whether any study instruments are redundant and can be eliminated, we will run a series of linear regressions with one instrument score as the dependent variable and the other instruments and demographic variables as independent variables. This would take the form of the following, for example, where the Confusion Assessment Method (CAM) is the dependent variable for the first regression then becomes an independent variable for the second regression (and the FRAIL score becomes the dependent variable):

Regression 1: CAM =

$$\alpha + \beta_1 \text{demographics (age, comorbidity, gender, race, etc)} + \beta_2 \text{FRAIL} \\ + \beta_3 \text{Katz} + \beta_4 \text{MoCA} + \beta_5 \text{Trail Making} + \beta_6 \text{CERAD} + \beta_7 \text{Pain} \\ + \beta_8 \text{Carolinas Comfort Scale}$$

Regression 2: FRAIL =

$$\alpha + \beta_1 \text{demographics} + \beta_2 \text{CAM} + \beta_3 \text{Katz} + \beta_4 \text{MoCA} + \beta_5 \text{Trail Making} \\ + \beta_6 \text{CERAD} + \beta_7 \text{Pain} + \beta_8 \text{Carolinas Comfort Scale}$$

.
.

.

Additional regressions until all instruments have been tested

This process is repeated until all survey instruments have served as a dependent variable. We will calculate the adjusted R-squared for each regression, and this exceeds 40% (40% of the variance for that instrument is explained by the combination of participant demographics and other instruments), then that instrument is considered redundant and will be eliminated for future participants.²² Standard regression diagnostics will be used and we will consider fractional polynomial modeling of all continuous variables as previously described.³¹

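### The 40% rule for dropping an instrument counts variance explained by demographics, although the plan defines redundancy by what the other instruments explain

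*Combined protocol and SAP*

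**What the plan says.** Section 9.4.1, outcome 6, makes each instrument in turn the dependent variable of a linear regression, "with the scores of all other instruments used as predictors, along with demographic information". Any instrument whose R-squared "exceeds 40% will be eliminated". The reason given is that "the other surveys explain a substantial portion of the information contained within that instrument".

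Section 9.5.1 writes the models out. The demographic terms are age, comorbidity, gender and race, with the list left open. The decision statistic is the adjusted R-squared, and the section explains the cut as "40% of the variance for that instrument is explained by the combination of participant demographics and other instruments". An instrument above it is no longer given to later participants.

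Elsewhere redundancy is described without demographics:
- Section 1.1: "the other instruments may predict a substantial portion of variance". Section 9.1.4, outcome 6, repeats this.
- Section 9.1.3: "the other measures explain a substantial portion of one measure's variance".
- Table 2 in section 9.4.1: "Predict explained variance (R-squared) of each instrument from scores of other instruments".

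The rule is applied at 25% and 75% of planned enrollment.

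**The concern.** The pass mark is set on one quantity and justified by another. A survey can safely be removed if the remaining surveys still capture what it measured. Age, comorbidity, gender and race are known before the operation and do not change with recovery, so they cannot replace a postoperative score or show a difference between anesthesia arms. Under the written rule, variance that they explain still counts toward removal.

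The instruments at risk include the Carolinas Comfort Scale, Katz, MoCA, Confusion Assessment Method, Trail Making and pain scores. These are the secondary clinical outcomes. Removal is mandatory, and neither section exempts an outcome instrument or asks for a separate survey-only figure. A drop at the first look would leave the outcome uncollected in up to 60 of 80 participants, and at the second look in about 20. Those data could not be recovered.

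**Working it through.** **Inputs from the documents.** Enrollment is 80 (section 9.2.1), so the looks fall at 0.25 × 80 = 20 and 0.75 × 80 = 60. The cut is 40% on adjusted R-squared (9.5.1). Four demographic terms are named. The example regression has seven other instruments. One of these, CERAD, is not in the schedule of evaluations, which leaves six.

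**Assumptions.** One complete set of scores per participant; four demographic and six instrument terms; independent normal predictors. The share of variance due to demographics is not in the documents, so a range is shown.

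**No plan figure to reproduce.** The 40% is a chosen cut-off, not a derived one.

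**Step 1: what the cut requires.** Adjusted R² = 1 − (1 − R²)(n − 1)/(n − k − 1), so the raw R² needed is 1 − 0.6(n − k − 1)/(n − 1).
- n = 20, k = 10: 1 − 0.6 × 9/19 = 0.716. With nothing explained by any term, the beta distribution of R² gives probability 0.117 of passing.
- n = 20, k = 6 (instruments only): 1 − 0.6 × 13/19 = 0.589, probability 0.041.
- n = 60, k = 10: 1 − 0.6 × 49/59 = 0.502, probability 0.00006.

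Part of the risk at n = 20 is therefore estimation noise. At n = 60 almost none is.

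**Step 2: probability of elimination when the surveys explain 0%** (simulation).

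| Demographic share (assumed) | As written, n = 20 | As written, n = 60 | Instruments alone, n = 20 | Instruments alone, n = 60 |
|---|---|---|---|---|
| 10% | 0.17 | at most about 0.01 | 0.04 | 0.00 |
| 20% | 0.27 | 0.04 | 0.04 | 0.00 |
| 30% | 0.38 | 0.18 | 0.04 | 0.00 |
| 45% | 0.60 | 0.66 | 0.04 | 0.00 |

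With seven other instruments, the 45% row as written becomes 0.60 and 0.63.

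**Step 3: mixed case.** With demographics at 30% and surveys at 20%, the written rule eliminates with probability about 0.66 (n = 20) and 0.81 (n = 60). Instruments alone give about 0.19 and 0.03.

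**Step 4: is real overlap still found?** With demographics at 0% and surveys at 45%, the two rules agree at n = 60: about 0.66 as written and 0.67 on instruments alone.

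**The case against.** Including demographics looks deliberate. Section 9.5.1 states the joint definition openly, section 9.4.1 also argues that an eliminated instrument adds little information, and demographics remain on file after a survey is dropped. The method is attributed to a cited text that cannot be consulted here. This shows intent, but 9.5.1 gives no reason for counting demographics and the reason in 9.4.1 names only the surveys.

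The objection to the size carries more weight. At n = 60 the harm is small unless demographics explain a good deal: with no survey overlap it is at most about 0.01 at a 10% share and 0.04 at 20%. Some instruments are also less exposed. Trail Making is normalized for age and education (9.4.2), and the Carolinas Comfort Scale and the pain question concern the hernia.

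A reader might infer that the pilot is likely to lose a cognitive or functional outcome, or that the multisite trial will be recommended without one. The documents support neither. They give no demographic R-squared. Section 9.5.1 removes instruments for later participants only, and section 9.1.4 (outcome 7) chooses the multisite primary outcome by weighing sample size against clinical significance.

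A reader might also conclude that the cut should go on the partial R-squared of the instruments given demographics. That is again not the quantity the plan describes. With demographics at 45% and surveys at 25% of total variance (n = 60), it eliminates in 0.69 of runs, against 0.08 for instruments alone. If the surveys truly explain 50% of the instrument but share 10, 20 or 30% of their own variance with age, it detects the overlap in only 0.38, 0.14 and 0.05 of runs, against about 0.83 for instruments alone.

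**Conclusion.** The mismatch stands. For a primary pilot outcome, the plan holds two versions of one elimination rule, and they can give different decisions. The version in the regression text can remove an outcome instrument that no remaining survey duplicates.

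How often this would happen is unknown. Over assumed demographic shares of 10 to 45% with no survey overlap, the probability runs from at most about 0.01 to 0.66 at 60 participants, and from about 0.17 to 0.60 at 20. On the other instruments alone it is about 0.00 and 0.04. These figures rest on the assumed shares, the number of terms and independent predictors; the conflict between the passages does not. It should be settled before the 25% look, when the rule is first applied.

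**What to change.** In section 9.4.1 (outcome 6) and section 9.5.1, apply the 40% cut to the adjusted R-squared from a regression on the other instruments alone, as Table 2 already describes. Report the R-squared with demographics added beside it as descriptive, and state that it does not count toward elimination. Bring the wording of 9.4.1, Table 2 and 9.5.1 into line, including that the statistic is the adjusted R-squared.

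The cost is one extra regression per instrument and a sentence or two in each place. The downside is that fewer instruments may be declared redundant, so the time burden on participants may fall less than hoped. The change does not cure the instability of R-squared at 20 participants: about 0.04 of non-overlapping instruments would still be dropped at that look.

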9.4.2 Secondary outcomes

Timing of measurements for secondary outcomes is outlined in the schedule of evaluations (section 6.1). Instruments are briefly summarized in [Table 3](#) below.

- 1) Outcome: Quality of life
 - a. Measurement: The Carolinas Comfort Scale (CCS) was developed specifically to measure quality of life in patients having hernia repair.²³ The instrument consists of 8 items on a 6-point Likert-type scale. The Cronbach's alpha was 0.979 in the original development paper and 0.95 on a subsequent international validation study.²¹ The CCS demonstrates superior discrimination when compared to generic quality of life instruments (SF-36), with reasonable test-retest reliability (kappa coefficients for questions range from 0.40-0.60 for all but 1 item. Additionally, the CCS is used as the primary quality of life instrument for the International Hernia Mesh Registry because it can be rapidly administered, is well accepted by patients, is highly reliable, and typically has only 10-15% missing data when used for the international registry.²¹ The CCS can be scored as a summary of all items and as a binary score for the presence or absence of symptoms. We will use a 0.5 standard deviation difference on the continuous scale as the minimal clinically important difference.²⁴
 - b. Timing: The CCS will be measured at baseline, 48 hours after surgery, at 2 weeks after surgery, and at 6 months after surgery.
- 2) Outcome: Physical function
 - a. Measurement: We will measure independence in activities of daily living with the 6-item Katz Index, a long-established measure for physical/functional status for individuals expected to have at least some degree of disability.²⁵ Prior work demonstrates coefficients of scalability ranging from 0.74-0.88, indicating the Katz Index offers a useful cumulative scale.²⁵ We will score the instrument on a 0-6 scale, indicating the number of activities where the participant is partially or fully dependent. A 0.5 standard deviation difference will again represent the minimal clinically important difference.²⁴
 - b. Timing: Measurement will occur at baseline, at 2 weeks after surgery, and at 6 months after surgery.
- 3) Outcome: Cognitive function and delirium
 - a. Measurement
 - i. Confusion Assessment Method (CAM) short form: The CAM is the most widely used instrument for detection of delirium, with typical sensitivity of 94% and specificity of 89% across multiple studies.²⁶ The instrument is scored on a 7-point scale and we will consider a 0.5 standard deviation difference as the minimal clinically significant difference.²⁴ Items include evaluation of attention, disorganized thinking, and altered levels of consciousness.
 - ii. Montreal Cognitive Assessment (MoCA) 5-minute form: The MoCA is a widely used tool for detection of dementia and other cognitive impairment, and is sensitive when used as a global cognitive screening tool.²⁷ The 5-minute form was developed to (1) reduce the significant time burden of the longer version which typically takes 15 minutes to complete, while (2) maintaining the psychometric advantages of the longer form, and (3) facilitating assessment by

telephone rather than in-person interviews. The instrument evaluates memory/attention, language fluency, orientation, and recall. The 5-minute MoCA has strong correlation with the full version ($r=0.87$), maintains the discrimination of the full version (area under the curve 0.78 versus 0.75 for full version, $p>0.05$), and has strong test-retest validity (intraclass correlation coefficient 0.89).²⁷ Since the 5-minute MoCA was also developed for testing by phone or in person, it meshes with our protocol plans to conduct immediate and long-term follow up by phone. A difference of 3 points is typically considered clinically significant.²⁷

- iii. Trail Making Tests Parts A and B: The Trail Making Test is one of the most popular neuropsychological tests for detecting processing speed, attention, and visual scanning.²⁸ Part A requires participants to draw a line between circles containing numbers, and the circles must be connected in numerical order. Part B is similar, but alternates letters and numbers (1, A, 2, B, et). Both items are scored as time to completion and then normalized to population data based on age and education.²⁸ To address ceiling effects on Part B, we will use the efficiency score for individuals who do not complete the instrument in <300 seconds.²⁹ A 0.5 standard deviation difference in time is considered clinically significant.²⁸
 - b. Timing: All measures will be administered at baseline, prior to discharge, at 48 hours after discharge, at 2 weeks after surgery, and at 6 months after surgery
- 4) Outcome: Pain
- a. Measurement: We will use a 10-point visual analog scale to measure overall pain levels. A 0.5 standard deviation will be considered a clinically significant difference.
 - b. Timing: Overall pain will be measured at baseline, prior to discharge, at 48 hours after surgery, at 2 weeks from surgery, and at 6 months from surgery.
- 5) Outcome: Postoperative complications
- a. Measurement: All complications will be recorded based on VA Surgical Quality Improvement Program definitions.³⁰ For complications not defined in VASQIP, definitions are also provided below.
 - i. Allergic reaction: if patients develop hives (raised red lesions) or a significant and persistent rash after administration of local or general anesthesia, this will be managed per the usual hospital protocol. Patients will receive a combination of epinephrine, corticosteroids, and antihistamines. Any patient with an allergic reaction will also be admitted for 24 hour observation that includes monitoring of vital signs, and blood pressure support with intravenous fluids. If the allergic reaction occurs during the operation, then the surgery will be canceled along with all assessments and will be rescheduled after it is determined that the operation can be performed safely without the allergic reaction.
 - ii. Hematoma or seroma: a collection of fluid in the tissues over the

incision site or in the scrotum that is detected on physical exam constitutes either a seroma or hematoma. If minimal symptoms present, this will be managed by observation. If persistent and significant symptoms occur, the seroma/hematoma will initially be managed by aspiration under local anesthesia up to two times. If the symptoms persist after aspiration, then the patient can be taken back to the operating room for surgical evacuation.

- iii. Injury to vessel: during dissection and/or mesh placement, there is the possibility of injury to the femoral or inferior epigastric vessels. If bleeding occurs at these vessels that cannot be resolved by applying pressure, this will be categorized as vascular injury. The inferior epigastric vessel is typically ligated without consequence if injured. Injury to femoral vessels will result in consult to vascular surgery for repair.
- iv. Neuralgia/chronic pain: if patients experience pain at/near the site of surgery for >3 months after the operation, they are considered to have neuralgia. This will be managed initially by consultation with the pain service for injection of steroids and local anesthetic at the site for up to 3 times. If this proves unsuccessful, the patient will be considered for surgical neurectomy.
- v. Spermatic cord injury or orchitis: during surgical repair, the spermatic cord (including vas deferens, spermatic artery, venous plexus) are mobilized away from the hernia sac. If the surgeon identifies injury (division of the vas deferens, bleeding from artery or veins that requires intervention beyond holding pressure) or if there is involution of the testicle on the side of the surgery (identified by pain beyond the ordinary, swelling in the groin, ultrasound showing no flow) then we will categorize as a spermatic cord injury. Intraoperatively, a vas deferens injury will result in consultation of urology for repair. Arterial and venous injuries are generally too small to repair intraoperatively, but vascular surgery service can be consulted for evaluation. Postoperatively, there is no treatment for cord injury other than pain control, urologic evaluation, and possible removal of testicle on the injured side.
- vi. Urinary retention: per our standard hospital protocol, if patients are unable to urinate by four hours after surgery, we will perform a bladder scan. If >200 mL of urine is seen, the patient will receive an in-and-out catheterization followed by observation for up to an additional four hours. If the patient is still unable to urinate, they will have a Foley catheter placed, be admitted for overnight observation, and be evaluated by urology. Typically, the patient goes home with a Foley leg bag and undergoes urodynamic testing 1 to 2 weeks later after being discharged with medication for benign prostatic hypertrophy. The occurrence of urinary retention will not change the study intervention regimen or the schedule of participant assessments.

- vii. Reoperation: Any unplanned surgery after the participant leaves the operating room following repair of the hernia.
- viii. Unplanned readmission or emergency room visit: Any admission for a planned outpatient surgery, or any hospital admission or emergency room visit that occurs after discharge.
- ix. Cardiac arrest requiring cardiopulmonary resuscitation: The absence of cardiac rhythm or presence of chaotic cardiac rhythm that results in loss of consciousness requiring the initiation of any component of basic and/or advanced cardiac life support.
- x. Myocardial infarction: A new transmural acute myocardial infarction occurring during surgery or within 14 days following surgery as manifested by new Q-waves on ECG.
- xi. Cerebral vascular accident/stroke: Patient develops an embolic, thrombotic, or hemorrhagic vascular accident or stroke with motor, sensory, or cognitive dysfunction (e.g., hemiplegia, hemiparesis, aphasia, sensory deficit, impaired memory) that persist for 24 or more hours.
- xii. Peripheral nerve injury: Peripheral nerve damage may result from damage to the nerve fibers, cell body, or myelin sheath during surgery. Peripheral nerve injuries (e.g., motor, sensory, and mixed motor/sensory injury) to the cervical plexus, brachial plexus, ulnar plexus, lumbar-sacral plexus (sciatic nerve), perineal nerve, and/or the femoral nerve should be included.
- xiii. Clostridium difficile infection: C. difficile-associated disease occurs when the normal intestinal flora is altered, allowing C. difficile to flourish in the intestinal tract and produce a toxin that causes a watery diarrhea. C. difficile diarrhea is confirmed by the presence of a toxin in a stool specimen. Answer yes only if you have a positive culture for C. difficile with a toxin assay and/or diagnosis of C. difficile documented in the chart.
- xiv. Bleeding requiring >4 units packed red blood cells
- xv. Deep vein thrombosis: The identification of a new blood clot or thrombus within the venous system, which may be coupled with inflammation. This diagnosis is confirmed by a duplex, venogram or CT scan. The patient must be treated with anticoagulation therapy, and/or placement of a vena cava filter or clipping of the vena cava.
- xvi. Pulmonary embolism: Lodging of a blood clot in a pulmonary artery with subsequent obstruction of blood supply to the lung parenchyma. The blood clots usually originate from the deep leg veins or the pelvic venous system. Enter "YES" if the patient has a V-Q scan interpreted as high probability of pulmonary embolism or a positive pulmonary arteriogram or positive CT scan. Treatment usually consists of: (a) Initiation of anticoagulation therapy, (b) Placement of mechanical interruption (e.g. Greenfield Filter), for patients in whom anticoagulation is contraindicated or already instituted.
- xvii. Systemic sepsis: If the primary physician or the chart states that the

- patient had systemic sepsis within the 30 days postoperatively, choose from the following choices for sepsis. If neither is present follow these definitions and choose the most applicable: (1) Sepsis: Definitive evidence of infection, plus evidence of a systemic response to infection. This systemic response is manifested by TWO or more of the following conditions: Temp >38 degrees C or <36 degrees Celsius; Septic Shock: Sepsis with hypotension despite adequate fluid resuscitation combined with perfusion abnormalities that may include, but are not limited to, lactic acidosis, oliguria, or an acute alteration in mental status. Patients who are on inotropic or vasopressor agents may not be hypotensive at the time that perfusion abnormalities are measured. HR >90 bpm, RR >20 breaths/min or PaCO₂ <32 mmHg(<4.3 kPa), WBC >12,000 cell/mm³, <4000 cells/mm³, or >10% immature (band) forms
- xviii. Prolonged ileus: Ileus is obstruction of the intestines from a variety of causes including mechanical obstruction, peritonitis, adhesions, or post-surgically as a result of functional dysmotility by the bowel. Bowel obstruction is any hindrance to the passage of the intestinal contents. Prolonged ileus or obstruction is defined as longer than 5 days postoperatively.
 - xix. Pneumonia: Inflammation of the lungs caused primarily by bacteria, viruses, and/or chemical irritants, usually manifested by chills, fever, pain in the chest, cough, purulent, bloody sputum. Enter "YES" if the patient has pneumonia meeting the CDC definition of pneumonia below AND pneumonia not present preoperatively. Pneumonia must meet one of the following TWO criteria: Criterion 1. Rales or dullness to percussion on physical examination of chest AND any of the following: a. New onset of purulent sputum or change in character of sputum, b. Organism isolate from blood culture, c. Isolation of pathogen from specimen obtained by transtracheal aspirate, bronchial brushing, or biopsy OR Criterion 2. Chest radiographic examination shows new or progressive infiltrate, consolidation, cavitation, or pleural effusion AND any of the following: a. New onset of purulent sputum or change in character of sputum, b. Organism isolated from the blood, c. Isolation of pathogen from specimen obtained by transtracheal aspirate, bronchial brushing, or biopsy, d. Isolation of virus or detection of viral antigen in respiratory secretions, e. Diagnostic single antibody titer (IgM) or fourfold increase in paired serum samples (IgG) for pathogen, f. Histopathologic evidence of pneumonia
 - xx. Failure to wean off ventilator or reintubation within 48 hours: If the patient remains intubated following completion of surgery for a period of ≥48 hours or is reintubated within 48 hours of surgery completion.
 - xxi. Urinary tract infection: Postoperative symptomatic urinary tract infection must meet one of the following TWO criteria from the

CDC definition:

1. One of the following: fever (>38 degrees C), urgency, frequency, dysuria, or suprapubic tenderness AND a urine culture of > 10⁵ colonies/ml urine with no more than two species of organisms OR
 2. Two of the following: fever (>38 degrees C), urgency, frequency, dysuria, or suprapubic tenderness AND any of the following:
 - Dipstick test positive for leukocyte esterase and/or nitrate
 - Pyuria (>10 WBCs/cc or > 3 WBC/hpf of unspun urine)
 - Organisms seen on Gram stain of unspun urine
 - Two urine cultures with repeated isolation of the same uropathogen with >10² colonies/ml urine in non-voided specimen
 - Urine culture with < 10⁵ colonies/ml urine of single uropathogen in patient being treated with appropriate antimicrobial therapy
 - Physician's diagnosis
 - Physician institutes appropriate antimicrobial therapy
- xxii. Acute renal failure: In a patient who did not require dialysis preoperatively, worsening of renal dysfunction postoperatively requiring hemodialysis, ultrafiltration, or peritoneal dialysis. If the patient refuses dialysis but is deemed to have required it by the care team, this complication is coded as present.
- xxiii. Progressive renal insufficiency: The reduced capacity of the kidney to perform its function as evidenced by a rise in creatinine of >2 mg/dl from preoperative value, but with no requirement for dialysis.
- xxiv. Wound disruption or dehiscence: Separation of the layers of a surgical wound, which may be partial or complete, with disruption of the fascia.
- xxv. Superficial surgical site infection: Infection that occurs within 30 days after the operation and infection involves only skin or subcutaneous tissue of the incision and at least one of the following:
 - Purulent drainage, with or without laboratory confirmation, from the superficial incision.
 - Organisms isolated from an aseptically obtained culture of fluid or tissue from the superficial incision.
 - At least one of the following signs or symptoms of infection: pain or tenderness, localized swelling, redness, or heat and superficial incision is deliberately opened by the surgeon, unless incision is culture-negative.
 - Diagnosis of superficial incisional SSI by the surgeon or attending physician. Do not count the following conditions as SSI:
 - Stitch abscess (minimal inflammation and discharge confined to the points of suture penetration).
 - Incisional SSI that extends into the fascial and muscle layers (see deep incisional SSI).
- xxvi. Organ space surgical site infection: An infection that occurs within

30 days after the operation and the infection appears to be related to the operation and the infection involves any part of the anatomy (e.g. organs or spaces), other than the incision, which was opened or manipulated during and operation and at least one of the following:

- Purulent drainage from a drain that is placed through a stab wound into the organ/space
- Organisms isolated from an aseptically obtained culture of fluid or tissue in the organ/space
- An abscess or other evidence of infection involving the organ/space that is found on direct examination, during reoperation, or by histopathologic or radiologic examination
- Diagnosis of an organ/space SSI by a surgeon or attending physician

xxvii. Deep wound surgical site infection: infection that occurs within 30 days after the operation and the infection appears to be related to the operation and infection involved deep soft tissues (e.g., fascial and muscle layers) of the incision and at least one of the following:

- Purulent drainage from the deep incision but not from the organ/space component of the surgical site.
- A deep incision spontaneously dehisces or is deliberately opened by a surgeon when the patient has at least one of the following signs or symptoms: fever (> 38 C), localized pain, or tenderness, unless site is culture-negative.
- An abscess or other evidence of infection involving the deep incision is found on direct examination, during reoperation, or by histopathologic or radiologic examination.
- Diagnosis of a deep incision SSI by a surgeon or attending physician.

-Note:

- Infection that involves both superficial and deep incision sites will be categorized as deep incisional SSI.
- An organ/space SSI that drains through the incision will be categorized as a deep incisional SSI.

b. Timing: Postoperative complications will be assessed prior to discharge and at the 2 week postoperative visit. Complications will be coded as present if identified at any time between the surgery and the 2 week visit.

6) Outcome: Operative and anesthesia times

- a. Measurement: Operative time will be recorded as the difference, in minutes, between the time of skin/wound closure and the time of surgical incision. Anesthesia time will be recorded as the difference, in minutes, between the time patients exit the operating room and the time of entrance to the operating room.
- b. Timing: Anesthesia intraoperative records routinely capture all four time points necessary to calculate the above outcomes. Records are scanned into the electronic medical record on the day of surgery and this data will be entered into the research record by research assistants on the day of surgery

(once the operation is complete).

- 7) Outcome: Recovery time (time spent in the post-anesthesia care and stepdown units)
- a. Measurement: Immediately following surgery, patients are typically transported directly to the post-anesthesia recovery unit for close monitoring by nursing staff and anesthesia faculty. Once the effects of anesthesia have diminished and patients are able to stay awake and maintain oxygenation without additional stimuli, they are transported to the stepdown unit for a period of observation to ensure they are able to ambulate and tolerate oral intake without nausea or vomiting. Time in the post-anesthesia care unit will be recorded as the difference between time of transport to the stepdown unit and the time of exit from the operating room. Time in the stepdown unit will be calculated as the difference between the time patients are discharged from the hospital (typically on the same day as surgery) and the time of transport from the post-anesthesia care unit. If patients are admitted rather than being discharged home on the same day as surgery, then stepdown time will be calculated as the difference between arrival in the inpatient or observation unit and the time of entrance to the stepdown unit. All values will be calculated in minutes.
 - b. Timing: These values will be calculated on the day of surgery by research assistants.

Table 3. Analysis of secondary (clinical outcomes)		
Outcome	Measurement	Number of items & time to completion
Quality of life	Carolinas Comfort Scale	8 items Time to completion: 1 minute
Physical function	Katz index	6 items Time to completion: 2 minutes
Cognitive function	1) Confusion Assessment Method (short form) 2) Montreal Cognitive Assessment 5-minute form 3) Trail Making Test Parts A and B	1) 4 items, time to completion 5 minutes 2) 8 items, time to completion 5 minutes 3) 2 trails, time to completion 2 minutes
Pain	Visual Analog Scale	1 item Time to completion: 10 seconds
Postoperative complications	VA Surgical Quality Improvement Program definitions	Complications outlined above Assessed by research assistants and not participants
Operative and anesthesia times	Time from anesthesia note	Assessed by research assistants and not participants

Recovery time in post-anesthesia care unit and stepdown unit	Timer by research assistant	Assessed by research assistants and not participants
--	-----------------------------	--

State and define the secondary outcome measures.

